### **Time to hospital discharge (Actual and Medical Equivalence)**

Time to actual hospital discharge is defined as duration of hospitalization from Day 1 through Day 29 that is recorded on eCRF All Visits page “General Duration of Hospitalization, & Overall Requirement for Mechanical Ventilation, ICU Admission and/or Oxygen Supplementation”. The proportion of subjects who are discharged from the hospital will be estimated using the CIF. Deaths that occur prior to discharge from the hospital will be treated as a competing risk. The estimated cumulative incidence and associated two-sided 95% CI on Days 15 and 29 will be displayed. Test for equality of the CIF between treatment groups will be conducted using Gray’s test.

Additionally, medical equivalence of hospital discharge date will be recorded on the eCRF if it is

different from the actual hospital discharge date, and the time to medical equivalence of hospital discharge will be analyzed using the same method as described above. The proportion of subjects who are medical equivalence of discharge from the hospital will be estimated using the CIF. Deaths that occur prior to medical equivalence of hospital discharge will be treated as a competing risk. The estimated cumulative incidence and associated two-sided 95% CI on Days 15 and 29 will be displayed. Test for equality of the CIF between treatment groups will be conducted using Gray's test.

### **Duration of Hospitalization (Actual and Medical Equivalence)**

The duration (number of days) of hospitalization from post-randomization through Day 29 will be calculated based on hospital admission and discharge (actual and medical equivalence) dates recorded on the eCRF. Number of days in the hospital will be compared between treatment groups using an ANOVA model, including number of days in the hospital as a dependent variable and treatment group as a fixed effect. From this model, the LS means and 95% CIs for each treatment group, the treatment difference in the LS means, the 95% CI for the difference, and the associated p-value will be presented. If appropriate, an ANCOVA model may instead be used to additionally adjust for baseline characteristics such as age and gender.

Subjects who died while in the hospital will be assigned as in the hospital for the number of days remaining from the day of death to Day 29 for the analysis. Subjects who were in the hospital at study completion will be assigned a hospitalization end date equals to the date of completion for the purpose of deriving the duration of hospitalization.

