### 2.2.2 Secondary Efficacy Endpoints

The secondary efficacy endpoints include the following:

- Time to actual ICU discharge: defined as duration of ICU stay from Day 1 through Day 29
  - Additionally, time to a medical equivalence of ICU discharge will be recorded and analyzed (defined as the time point when the patient no longer requires ICU level care, ie, not requiring invasive mechanical ventilation, or intensive monitoring such as arterial line or central line placement, administration of IV vasopressors to support blood pressure, or O2 supplementation greater than that delivered by nasal cannula)
- Duration of mechanical ventilation from Day 1 through Day 29
- Time to actual hospital discharge: defined as duration of hospitalization from Day 1 through Day 29
  - Additionally, time to a medical equivalence of hospital discharge will be recorded and analyzed (defined as the time point when the patient no longer requires supplemental oxygen and no longer requires ongoing medical care [yet may not be discharged from hospital for social or quarantine reasons])
- Duration of any oxygen use Day 1 through Day 29
- Absolute value and mean change from baseline in the Ordinal scale Day 1 through Day 29

The Ordinal scale is as follows:

- 1) Death;
- 2) Hospitalized, on invasive mechanical ventilation or extracorporeal membrane oxygenation (ECMO);
- 3) Hospitalized, on non-invasive ventilation or high flow oxygen devices;
- 4) Hospitalized, requiring supplemental oxygen;
- 5) Hospitalized, not requiring supplemental oxygen;
- 6) Not hospitalized, limitation on activities;
- 7) Not hospitalized, no limitations on activities.

- Proportion (percentage) of subjects in each severity category of the 7-point Ordinal scale at Day 15 and Day 29
- Number of subjects who develop Acute Respiratory Distress Syndrome (ARDS) overall and distribution by severity through Day 29
- Change from baseline in SOFA score at Day 5, Day 15, and Day 29

- Assessment of Clinical Severity: Change in NEWS from baseline (Day 1 through Day 29).  
The NEWS has demonstrated an ability to discriminate patients at risk of poor outcomes. This score is based on 7 clinical parameters (respiration rate, oxygen saturation, any supplemental oxygen, temperature, systolic blood pressure, heart rate, level of consciousness [Alert, Voice, Pain, Unresponsive]).
- Time to clinical response: NEWS  $\leq 2$  maintained for 24 hours, Day 1 through Day 29

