### 3. INVESTIGATIONAL PLAN

#### 3.1 Study Design

This is a prospective, multi-center, randomized (1:1), open-label, pilot study of high dose IVIG plus SMT versus SMT alone in subjects with COVID-19 who are hospitalized and require ICU admission. The first 6 subjects randomized will be staggered with an interval of no less than 1 week between subjects. If there are no definitely related SAEs reported 1 week after the randomization of the 6th subject, competitive enrollment would ensue thereafter. If a definitely related SAE were to be reported among these 6 subjects, the Study-Independent Safety Review Committee (SISRC) would carefully review and evaluate the case and make appropriate recommendations with regard to study status.

In this study, symptomatic subjects with positive PCR (RT-PCR) or other FDA-approved or regulatory-authority-approved diagnostic assay for SARS-CoV-2 in any specimen during the current hospital admission prior to randomization will receive SMT or SMT plus a net total dose of IVIG of 2 g/kg (body weight) administered in divided doses over 4 to 5 consecutive days at the Principal Investigator (PI)'s discretion. The maximum dose will be capped at 160 g (equivalent to body weight of 80 kg).

[figure not shown]
Specifically, subjects randomized to combination high dose IVIG will receive the first intravenous (IV) infusion of IVIG on Day 1. The total net dose of 2 g/kg body (capped at a maximum of 160 g for subjects weighing more than 80 kg) will be administered in divided doses over consecutive days. At the discretion of the PI, the 2 g/kg net total dose may be divided either into (a) infusions of 500 mg/kg body weight over 4 days OR (b) 400 mg/kg body weight over 5 days.

Approximately 100 subjects (who meet the inclusion/exclusion criteria specified in Protocol Sections 5.1 & 5.2) will be randomized in a 1:1 (IVIG plus SMT : SMT alone) ratio with an interim analysis after 50 subjects (approximately 25 per group). There will be no interruption in study conduct during interim analysis as this simply represents sponsor safety due diligence.

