## 4. GENERAL CONSIDERATIONS FOR DATA ANALYSIS

Unless otherwise specified, continuous variables will be summarized using descriptive statistics (n, mean, standard deviation, median, minimum, and maximum). Categorical variables will be summarized showing the number and percentage of subjects within each category.

Summary results will be provided for each treatment group. All tabulations will be based on pooled data across centers.

All statistical tests will be two-sided and tested at the 5% level of significance.

Analyses will be performed using SAS for Windows statistical software, version 9.4 or higher (SAS, Cary, NC), except where other software may be deemed more appropriate. In the event that other software is used to perform some analyses, the details will be provided in the Clinical Study Report.

■ will perform all efficacy and safety analyses described in this SAP.

Subject data will be listed, sorted by treatment group and subject number. When applicable, listings will be additionally sorted by visit and assessment date/time.

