**Table 1 Missing Data and Competing Events Coding for Time to Event Data Analyses**

Endpoint	Right Censoring and Competing Events
Subject Survival	Subjects who are still alive as of the last known follow-up will be right censored as of the date of last subject contact when the subject was known to be alive.
Time to actual ICU Discharge or Medical Equivalence of ICU Discharge (if different from actual ICU discharge date)	Subjects who did not discharge or medical equivalence of discharge from the ICU at any time during follow-up will be right censored as of the date of last subject contact when the subject was known to be in the ICU. Subject death will be considered a competing event. Competing risk methods e.g., cumulative incidence function (CIF) will be used to account for competing events in the analysis.
Time to actual Hospital Discharge or Medical Equivalence of Hospital Discharge (if different from actual hospital discharge date)	Subjects who did not discharge or medical equivalence of discharge from the hospital at any time during follow-up will be right censored as of the date of last subject contact when the subject was known to be in the hospital. Subject death will be considered a competing event. Competing risk methods e.g., cumulative incidence function (CIF) will be used to account for competing events in the analysis.
Time to Clinical Response	Subjects who did not experience clinical response or died at any time during follow-up will be right censored as of the date of last non-missing assessment of NEWS on or prior to Day 29.

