## 6.2 Secondary Efficacy Endpoints and Analyses

### Time to ICU discharge (Actual and Medical Equivalence)

Time to actual ICU discharge is defined as duration of actual ICU stay from Day 1 through Day 29 that is recorded on the eCRF All Visits page "General Duration of Hospitalization, & Overall Requirement for Mechanical Ventilation, ICU Admission and/or Oxygen Supplementation". The proportion of subjects who are discharged from the ICU will be estimated using the CIF. Deaths that occur prior to discharge from the ICU will be treated as a competing risk. The estimated cumulative incidence and associated two-sided 95% CI on Days 15 and 29 will be displayed. Test for equality of the CIF between treatment groups will be conducted using Gray's test.

Additionally, medical equivalence of ICU discharge date will be recorded on the eCRF if it is different from the actual ICU discharge date, and the time to medical equivalence of ICU discharge will be analyzed using the same method as described above. The proportion of subjects who are medical equivalence of discharge from the ICU will be estimated using the CIF. Deaths that occur prior to medical equivalence of ICU discharge will be treated as a competing risk. The estimated cumulative incidence and associated two-sided 95% CI on Days 15 and 29 will be displayed. Test for equality of the CIF between treatment groups will be conducted using Gray's test.

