### **Duration of ICU stay (Actual and Medical Equivalence)**

The duration (number of days) of ICU stay from post-randomization through Day 29 will be calculated based on ICU admission and discharge (actual and medical equivalence) dates recorded on the eCRF. Number of days in the ICU will be compared between treatment groups using an ANOVA model, including number of days in the ICU as a dependent variable and treatment group as a fixed effect. From this model, the LS means and 95% CIs for each treatment group, the treatment difference in the LS means, the 95% CI for the difference, and the associated p-value will be presented. If appropriate, an ANCOVA model may instead be used to additionally adjust for baseline characteristics such as age and gender.

Subjects who died while in the ICU will be assigned as in the ICU for the number of days remaining from the day of death to Day 29 for the analysis. Subjects who were at ICU at study completion will be assigned an ICU end date equals to the date of completion for the purpose of deriving the number of ICU days.

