### **9. SAMPLE SIZE AND POWER CALCULATIONS**

Because of the urgency and lack of previous prospective COVID-19 data, sample size estimation remains incompletely defined; however the size of this pilot study is commensurate with other Phase 2 investigations ongoing during the COVID-19 pandemic. Approximately 100 subjects are allowed to be randomized as part of a humanitarian effort against COVID-19.

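### SAP completion and censoring rules for the medical-equivalence discharge endpoints follow where the subject is: read literally, they can override a recorded equivalence date and they censor a subject who leaves without equivalence on leaving

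*SAP*

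**What the plan says.** - **Definition.** SAP 2.2.2, like protocol 4.1.2, makes ME of hospital discharge a clinical state, "defined as the time point when the patient no longer requires supplemental oxygen and no longer requires ongoing medical care". It adds that such a subject may still be kept in for social or quarantine reasons. ME of ICU discharge is likewise the point at which ICU-level care is no longer needed.
- **Duration.** SAP 6.2 treats the actual and ME versions together, once for the hospital and once for the ICU. Each section first says that duration is computed from the recorded dates of both kinds. Each then gives one completion rule: "Subjects who were in the hospital at study completion will be assigned a hospitalization end date equals to the date of completion" for the hospital and "Subjects who were at ICU at study completion will be assigned an ICU end date equals to the date of completion" for the ICU. Neither is limited to subjects without an ME date. Deaths in the ICU or hospital are filled to Day 29, again without mention of ME.
- **Time to event.** SAP 6.2 estimates the cumulative incidence of ME with prior death as a competing event, and compares arms by Gray's test. On data capture it says "medical equivalence of ICU discharge date will be recorded on the eCRF if it is different from the actual ICU discharge date"; the hospital section matches.
- **Censoring.** SAP Table 1 uses one row per location for both versions. A subject without the hospital event "will be right censored as of the date of last subject contact when the subject was known to be in the hospital". The ICU row is parallel.

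**The concern.** The ME versions add information only for subjects whose clinical readiness and physical location part company. Those are the subjects for whom location-based rules give the wrong value.

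- A subject who is fit but still in a bed at completion can lose the recorded ME date in the duration ANOVA and receive the actual stay instead. That defeats the purpose of the ME duration.
- A subject who leaves without meeting ME, for example home on oxygen, or out of the ICU on more oxygen than a nasal cannula delivers, is censored on leaving. Oxygen use is still collected afterwards: daily in hospital, and at Days 15 and 29 after discharge. Collected data are discarded, and the censoring depends on prognosis, because leaving while still on oxygen says something about when ME will be reached.

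At stake are the ME duration comparison, the Day 15 and Day 29 ME incidences and Gray's test on them. The trial is open-label, so the derivations should be settled before the data are analysed.

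**Working it through.** There is no planned figure to reproduce. SAP 9 states that "sample size estimation remains incompletely defined", and the plan gives no SD or event rate for these endpoints.

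**1. Duration of a subject who is fit but held.** SAP 4.6: duration = end − start + 1. With randomization on Day 1, ME on Day 12 and completion on Day 29:

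- recorded ME date used: 12 − 1 + 1 = 12 days;
- completion rule applied literally: 29 − 1 + 1 = 29 days, an excess of 17.

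The Day 29 visit has a window of ±1 day, so the literal score is nominally 28 to 30. For ME on Day 5, 10, 15 or 20 the excess is 24, 19, 14 or 9 days.

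**2. Effect on an arm mean.** Shift = f × (29 − m), where f is the share of the arm held to completion and m is the ME day. Both are assumed.

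| f | m = 10 | m = 15 | m = 20 |
|---|---|---|---|
| 2% | 0.38 | 0.28 | 0.18 |
| 5% | 0.95 | 0.70 | 0.45 |
| 10% | 1.9 | 1.4 | 0.9 |
| 20% | 3.8 | 2.8 | 1.8 |

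The treatment contrast moves only by the difference between the arms' shifts. With m = 15 and shares of 10% and 5%, that is 1.4 − 0.7 = 0.7 days; with equal shares and ME days it is zero.

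For scale: about 100 subjects "will be randomized in a 1:1 (IVIG plus SMT : SMT alone) ratio", so about 50 per arm, and "All statistical tests will be two-sided and tested at the 5% level of significance". The difference detectable with 80% power is SD × (1.960 + 0.842) × √(2/50) = 0.560 × SD. That is about 4.5, 5.6 or 6.7 days for assumed SDs of 8, 10 or 12.

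**3. Subject who leaves without ME.** Assume an arm of 50: 15 deaths on Day 12, 5 still in hospital on Day 29, k sent home on oxygen on Day 14 and not ME by Day 29, and the other 30 − k reaching ME evenly between Days 8 and 26. Day 29 ME incidence by the Aalen-Johansen estimator, under three treatments of the k subjects:

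- (a) blank ME field taken as the actual date: they are events, 30/50 = 0.600;
- (b) Table 1 read literally: censored on Day 14;
- (c) followed to Day 29 without ME: (30 − k)/50.

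For (b) with k = 5, 9 subjects reach ME and 15 die by Day 14. Incidence is then 9/50 = 0.180 and the event-free share is 26/50 = 0.520. Of the 21 left at risk, 16 reach ME, so incidence = 0.180 + 0.520 × 16/21 = 0.576.

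| k | (a) | (b) | (c) |
|---|---|---|---|
| 2 | 0.600 | 0.591 | 0.560 |
| 5 | 0.600 | 0.576 | 0.500 |
| 8 | 0.600 | 0.558 | 0.440 |

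Rule (b) implicitly gives the k subjects the later ME experience of those who stayed in hospital. It exceeds the fully followed value (c) by 3.1, 7.6 and 11.8 points.

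**4. Comparison within the SAP.** For mechanical ventilation and oxygen, SAP 6.2 ties the completion rule to support still ongoing, and the death rule to a missing stop date. The ICU and hospital duration sections contain neither condition.

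**The case against.** The best defence is that the completion rule is a fill-in, not an override. Both duration sections first say that ME dates are used, and a subject with a recorded ME date already has an end date. The ventilation and oxygen rules, which concern ongoing support, favour that reading. This stands in part: the 29-day score is what the sentence yields if followed as written, not a certain outcome. Nothing in the text excludes it, however.

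A reader might go further in four ways that the documents do not support.

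- *That time to ME is corrupted for held subjects.* It is not. That analysis has no completion override, and the subject is an event on the ME date.
- *That a subject sent home on oxygen is wrongly not counted as discharged.* For actual discharge the subject is an event. For ME the subject is a non-event because the clinical definition requires no supplemental oxygen. Only the censoring date is at fault.
- *That ordinary discharges drop out because their ME field is blank.* Recording the date only when it differs most naturally means that a blank equals the actual date. The gap is narrower: the same convention could count a subject still on oxygen as ME at discharge.
- *That ME can never come later than actual discharge.* No passage says so, and the definition is by clinical state.

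It is also fair to say that these are additional versions of secondary endpoints, in a pilot without multiplicity control.

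**Conclusion.** The point holds as a defect in the derivation rules. The shared completion rule, read literally, replaces a recorded ME date with the completion date for subjects who are fit but still in a bed: 17 days too many in the Day 12 example. This is confined to the duration ANOVA. The Table 1 rule censors subjects who leave without ME on leaving rather than at last follow-up. In the assumed arm this moves Day 29 ME incidence by about 3 to 12 points against full follow-up.

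The shares held, ME days, SDs, deaths and discharges on oxygen are all assumptions; the documents give none. No bias between arms has been shown. It arises only if the arms differ in the number or timing of these subjects. Actual-discharge endpoints and the primary mortality analysis are unaffected.

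**What to change.** Amend SAP 4.4 (Table 1), 4.6 and 6.2 for the ME versions only:

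1. Use the recorded ME date whatever the subject's location.
2. Apply the completion fill-in only when ME was not reached.
3. State how the death fill-in applies to a subject who reached ME and later died in the ICU or hospital. As written, ME on Day 12 and death in hospital on Day 20 is filled to Day 29.
4. State that a blank ME field means the actual discharge date only if the ME definition was met at discharge.
5. Censor subjects who leave without meeting ME at their last assessment up to Day 29.

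Do not redefine ME as the earlier of actual discharge and ME. That would count subjects who still need oxygen as equivalent and so change the endpoint in protocol 4.1.2 and SAP 2.2.2.

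The cost is a few lines of SAP text and one revised derivation. Item 4 may also need a check of ME status at discharge during data review, since the eCRF instructions are not in the documents.

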### **Duration of any oxygen use**

The duration (number of Days) of any oxygen use from Day 1 through Day 29 will be calculated based on the start/stop date of using oxygen supplementation recorded on the eCRF All Visits page "General Duration of Hospitalization, & Overall Requirement for Mechanical Ventilation, ICU Admission and/or Oxygen Supplementation". Number of days on oxygen will be compared between treatment groups using an analysis of variance (ANOVA) model, including number of days on oxygen as a dependent variable and treatment group as a fixed effect. From this model, the LS means and 95% CIs for each treatment group, the treatment difference in the LS means, the 95% CI for the difference, and the associated p-value will be presented. If appropriate, an analysis of covariance (ANCOVA) model may instead be used to additionally adjust for baseline characteristics such as age and gender.

Subjects who died during the hospitalization without a stop date of using oxygen supplementation recorded on the eCRF will be assigned as being on oxygen for the number of days remaining to Day 29 for the analysis. Subjects who had oxygen use ongoing at study completion will be assigned an oxygen use end date equals to the date of completion for the purpose of deriving duration of oxygen use. Subjects who never received supplemental oxygen through Day 29 will be included in the analysis with a value of zero days of oxygen use.

A listing of all supplemental oxygen and saturation ( $SpO_2$  and  $SaO_2$ ) data collected throughout the study will be provided.

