5 SELECTION AND WITHDRAWAL OF SUBJECTS

5.1 Inclusion Criteria

A subject must meet all the following inclusion criteria to be eligible for participation in this study:

1. Hospitalized male or female subjects of ≥ 18 years of age at time of Screening who are being treated in the ICU for COVID-19 for not longer than 48 hours or for whom a decision has been made that COVID-19 disease severity warrants ICU admission.
2. Has laboratory-confirmed novel coronavirus (SARS-CoV-2) infection as determined by qualitative PCR (reverse transcriptase [RT]-PCR), or other FDA-approved-or regulatory-

GRIFOLS Bioscience Industrial Group	Number	BLG-CL-PRT-000020	Version	4.0	Status	Effective	Effective Date	19-Jul-2021	41 of 91
	GC2007 - A Multicenter, Randomized, Open-label Parallel Group Pilot Study to Evaluate Safety and Efficacy of High Dose Intravenous Immune Globulin (IVIG) plus Standard Medical Treatment (SMT) versus SMT alone in						Page		

authority-approved diagnostic assay for COVID-19 in any specimen during the current hospital admission prior to randomization.

3. Illness (symptoms of COVID-19 of any duration requiring ICU level care), and the following:
 - a) Radiographic infiltrates by imaging (chest X-Ray, CT scan, etc.), AND
 - b) Requiring mechanical ventilation and/or supplemental oxygen.

Note: ICU level care is defined as the medical need for intensive or invasive monitoring; immediate or impending need for supportive care of the airway, breathing, or circulation; and/or stabilization of acute severe or life-threatening complications of COVID-19.
4. Any one of the following related to COVID-19: i. Ferritin > 400ng/mL, ii. LDH > 300 U/L, iii. D-Dimers > reference range, or iv. C-reactive protein (CRP) > 40 mg/L.
5. Subject provides informed consent prior to initiation of any study procedures.

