After all Screen/Baseline assessments are complete subjects may be randomized.

Subjects in the combination arm may receive the first infusion of Gamunex-C on Screen/Baseline and Randomized Treatment visit (Day 1) if eligibility criteria are met, and all pre-infusion assessments are performed. Subjects in the combination arm will receive a total of 2 g/kg Gamunex-C in divided doses. At the prerogative of the Principal Investigator the 2 g/kg dose may be divided into 4 days (500 mg/kg/day) or 5 consecutive days (400 mg/kg/day).

Vital signs will be monitored during Gamunex-C infusion. Vital signs will be measured within 1 hour prior to the start of Gamunex-C infusion, 30 minutes after the start of infusion, and hourly through the end of Gamunex-C infusion. If the systolic blood pressure measured within 1 hour prior to the start of Gamunex-C infusion is > 160 mm Hg, then measures to lower blood pressure below this threshold should be administered and documented prior to commencing Gamunex-C infusion. To commence the Gamunex-C infusion, the systolic blood pressure must be < 160 mm Hg.

7.2.3 SMT, Randomized IVIG Treatment, Daily Evaluations (Days 2 through 10 inclusive) and Additional Day 5±1 Day Assessments

All subjects receive continued SMT. Subjects randomized to IVIG plus SMT will receive the remainder of the net 2 g/kg dose in divided doses at the Principal Investigator's prerogative on consecutive days through Day 4 (500 mg/kg/day) or through Day 5 (400 mg/kg/day) to achieve the total dose of 2 g/kg body weight. Subjects receiving Gamunex-C infusions will have vital signs measured within 1 hour prior to the start of each Gamunex-C infusion, 30 minutes after the start of infusion, and hourly through the end of Gamunex-C infusion. If the systolic blood pressure measured within 1 hour prior to the start of Gamunex-C infusion is > 160 mm Hg, then measures to lower blood pressure below this threshold should be administered and documented prior to commencing Gamunex-C infusion. To commence the Gamunex-C infusion, the systolic blood pressure must be < 160 mm Hg.

Daily assessments include the following:

- Ordinal Scale assessment
- NEWS ([Appendix 2](#))
- Clinical features key symptoms: fever, cough, shortness of breath, fatigue, myalgia etc.
- Vital signs (temperature, systolic and diastolic blood pressure, pulse, respiratory rate)
- Record any supplemental oxygen administration (type, %, flow start/end date/time)

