- Record details of mechanical ventilation parameters (start/end date/time)
- Record oxygen saturation (specify on or off oxygen supplementation)
- Record daily 24-hour fluid balance (intake and output) while in hospital
- Record body weight for assessing fluid balance twice daily on Days 1 through 5 inclusive (at least 8 hours should separate the time from the first recorded weight)

GRIFOLS Bioscience Industrial Group	Number	BLG-CL-PRT-000020	Version	4.0	Status	Effective	Effective Date	19-Jul-2021	Page	51 of 91
	GC2007 - A Multicenter, Randomized, Open-label Parallel Group Pilot Study to Evaluate Safety and Efficacy of High Dose Intravenous Immune Globulin (IVIG) plus Standard Medical Treatment (SMT) versus SMT alone in									

- Record SAEs and TEAEs
- Record standard care concomitant medications

All laboratory tests and serum and plasma samples are required for all study subjects, regardless of treatment assignment. For subjects randomized to IVIG plus SMT all laboratory samples must be obtained prior to the Gamunex-C infusion on the designated day.

On Day 5 ± 1 day the following *additional* assessments will be performed:

- Assessment of ARDS (Berlin Criteria) ([Appendix 3](#))
- SOFA score ([Appendix 4](#))
- Respiratory sample for quantitative measurement of SARS-CoV-2 viral load by NAT or PCR (real-time RT-PCR) (obtained via nasopharyngeal swab)
- Sample for quantitative measurement of IgM and IgG antibodies to SARS-CoV-2 (store serum samples frozen at -70°C for later analysis at an external lab)
- Serum Chemistry (creatinine, albumin, ALT, total bilirubin, LDH)
- Ferritin (serum), D-dimer (plasma, sodium citrate tube), CRP (serum)
- Hematology: absolute lymphocyte count and standard hematology (hemoglobin, hematocrit, platelet count, leukocyte count with differential)
- DAT
- Cytokine panel (IL-1 β , IL-10, IL-6, IL-8, IL-2, interferon γ , and TNF- α). Note: serum samples must be stored at -70°C for later analysis at a reference laboratory.

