### **Duration of mechanical ventilation**

The duration (number of days) on mechanical ventilation from post randomization through Day 29 will be calculated based on the start/stop dates of mechanical ventilation recorded on the eCRF All Visits page “General Duration of Hospitalization, & Overall Requirement for Mechanical Ventilation, ICU Admission and/or Oxygen Supplementation”. Number of days on mechanical ventilation will be compared between treatment groups using an ANOVA model, including number of days on mechanical ventilation as a dependent variable and treatment group as a fixed effect. From this model, the LS means and 95% CIs for each treatment group, the treatment difference in the LS means, the 95% CI for the difference, and the associated p-value will be presented. If appropriate, an ANCOVA model may instead be used to additionally adjust for baseline characteristics such as age and gender.

Subjects who died during the hospitalization without a stop date of mechanical ventilation recorded on the eCRF will be assigned as being on mechanical ventilation for the number of days remaining to Day 29 for the analysis. Subjects who had mechanical ventilation ongoing at study completion will be assigned a mechanical ventilation end date equals to the date of completion for the purpose of deriving duration of mechanical ventilation. Subjects who are never placed on mechanical ventilation through Day 29 will be included in the analysis with a value of zero days on mechanical ventilation.

A listing of all mechanical ventilation and oxygen administration data collected throughout the study will be provided.

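### Oxygen days are derived from oxygen-supplementation dates alone, so ventilated days can drop out unless sites also enter ventilator oxygen in that record

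*SAP*

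**What the plan says.** SAP 2.2.2 lists the secondary endpoint as "Duration of any oxygen use Day 1 through Day 29". SAP 6.2 says that it will be "calculated based on the start/stop date of using oxygen supplementation recorded on the eCRF All Visits page". Three rules complete the derivation:

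- **Zero rule:** "Subjects who never received supplemental oxygen through Day 29 will be included in the analysis with a value of zero days of oxygen use".
- **Death rule:** it covers "Subjects who died during the hospitalization without a stop date of using oxygen supplementation recorded on the eCRF" and treats them as on oxygen for the days left to Day 29.
- **Ongoing rule:** oxygen still in use at study completion ends on the completion date.

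Arms are compared by ANOVA, or by ANCOVA if appropriate.

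Ventilation duration is a separate analysis in the same section, "calculated based on the start/stop dates of mechanical ventilation recorded on the eCRF All Visits page". The Protocol's daily assessments (7.2.3) list the two supports as separate items, "Record any supplemental oxygen administration (type, %, flow start/end date/time" and "Record details of mechanical ventilation parameters (start/end date/time", and the schedule in Protocol Appendix 1 gives each its own row. Inclusion criterion 3b (Protocol 5.1) reads "Requiring mechanical ventilation and/or supplemental oxygen".

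**The concern.** The endpoint is named for any oxygen use, but its only stated source is the oxygen-supplementation record. Neither document says that a ventilated day counts as an oxygen day. If a site closes the oxygen entry at intubation, or makes no oxygen entry for a subject who arrives ventilated, those days are not counted.

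Fewer days is the better result, so a subject who worsens to ventilation can score better than one who is weaned to room air. This affects survivors as well as deaths, so it is not only a question of how deaths are carried forward. If ventilation differs between the arms, the treatment comparison moves in favour of the arm with more of it.

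**Working it through.** The plan gives no effect size, power or expected mean for this endpoint, so there is no figure to reproduce. The check applies the SAP rules to constructed histories and then to arm means.

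**Inputs from the documents**
- Window Day 1 to Day 29 (SAP 2.2.2).
- Duration = end - start + 1 (SAP 4.6).
- Zero and death rules (SAP 6.2).
- About 100 subjects randomized 1:1, so about 50 per arm (Protocol 4.2).

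**Assumed:** all histories, ventilation shares and day counts below, and that ventilator time is not entered as oxygen.

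**Step 1. Single subjects**

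| History | As written | If ventilated days count |
|---|---|---|
| Never ventilated, oxygen Days 1-10, then room air | 10 - 1 + 1 = 10 | 10 |
| Survivor, oxygen Days 1-3, ventilated Days 4-29 | 3 - 1 + 1 = 3 | 29 - 1 + 1 = 29 |
| Survivor, ventilated Days 1-29, no oxygen entry | 0 (zero rule) | 29 |
| Oxygen Days 1-3 with stop date at intubation, dies ventilated Day 12 | 3 (death rule not triggered) | 29 (death rule applied to ventilation) |
| Ventilated from Day 1, dies in hospital, no oxygen entry | Undefined: the zero rule gives 0, the death rule carries to Day 29 | 29 |

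**Step 2. Arm means, moderate case**

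Bias in the difference of means = (difference in proportion ventilated) x (uncounted days per ventilated subject).
- 10 points: 0.10 x 10 = 1.0 days; 0.10 x 14 = 1.4 days.
- 5 points and 10 days: 0.05 x 10 = 0.5 days.
- 15 points: 0.15 x 10 = 1.5 days; 0.15 x 14 = 2.1 days.

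The bias favours the arm with more ventilation.

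**Step 3. Arm means, extreme case**

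Suppose the ventilated subjects are survivors ventilated on all 29 days with no oxygen entry. Each one lowers the mean of a 50-subject arm by 29/50 = 0.58 days. Take 10% such subjects in arm A, 20% in arm B, and 12 oxygen days for everyone else.
- As written: A = 0.90 x 12 = 10.8; B = 0.80 x 12 = 9.6; B - A = -1.2.
- Ventilation counted: A = 10.8 + 0.10 x 29 = 13.7; B = 9.6 + 0.20 x 29 = 15.4; B - A = +1.7.
- The gap is 1.7 + 1.2 = 2.9 = 0.10 x 29, as the Step 2 formula gives.

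With 8 to 16 oxygen days for the others and share pairs of 10/20%, 10/30% and 20/40%, B - A runs from -0.8 to -3.2 as written and from +1.3 to +4.2 with ventilation counted. The sign change is built into this case. With m oxygen days for the others and share difference d, the two results are -d x m and d x (29 - m), which have opposite signs for any m between 0 and 29. It shows that reversal is possible, not that it is likely.

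**The case against.** The strongest reply is that everything depends on a form that is not in the documents. The dates come from one combined eCRF page covering ventilation, ICU admission and oxygen. The oxygen record has fields for type, percentage and flow, which could hold oxygen given through a ventilator. If sites complete it that way, no days are lost.

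Some wording also leans toward an inclusive reading. NEWS has one yes/no item for supplemental oxygen and no ventilator item. Ordinal category 5 is the hospitalized subject who needs no supplemental oxygen. The Ordinal scale's split between ventilation (2) and supplemental oxygen (4) settles nothing, because it also splits off high-flow oxygen (3).

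The effect would also be visible in part. Ventilation duration is analysed separately, the Ordinal scale ranks ventilation below oxygen, and this is one of many secondary endpoints in a pilot without multiplicity adjustment.

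The dependence on entry practice stands, and it limits the point to what can happen. It does not remove the point. The SAP does not require ventilation to be entered as oxygen, the inclusive readings are inferences from other scales, and sites may differ.

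Two inferences that a reader might draw go too far:
- **That the zero rule can describe only a ventilated subject.** Criterion 3b points that way for eligible subjects, but the ITT population is everyone randomized, including anyone randomized in error. The sentence also mirrors the zero rule for ventilation and may be template text. An exact zero further needs no oxygen entry after extubation.
- **That closing the oxygen entry at intubation is what the forms direct.** The completion instructions cannot be seen. The documents permit this practice but do not prescribe it.

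**Conclusion.** The point holds as a gap in the derivation. As written, SAP 6.2 can score a ventilated survivor at 0 or 3 oxygen days where 29 would be expected, below the 10 of a subject weaned after Day 10. The death rule misses a subject whose oxygen entry was closed at intubation. It contradicts the zero rule for a subject who dies ventilated with no oxygen entry.

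The possible bias favours the arm with more ventilation. The 1.0-1.4 days illustration assumes a 10-point difference in subjects ventilated for 10-14 uncounted days, the same day count in both arms, and that ventilator time is not entered as oxygen. None of these comes from the documents.

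A reader might infer that the plan excludes ventilated days, or that the arm comparison will have the wrong sign. The documents support neither. They are silent on whether ventilated days count, and a reversal needs that entry practice, an imbalance in ventilation, and a true difference smaller than the bias.

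The SAP should be changed, but the primary mortality analysis is not affected.

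**What to change.** In SAP 6.2:

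1. Define oxygen days as the number of calendar days from Day 1 through Day 29 with supplemental oxygen, invasive or non-invasive ventilation, or extracorporeal support, taken as the union of the eCRF dates. Use a union, not a sum of spans: oxygen Days 1-4 plus ventilation Days 4-29 would sum to 4 + 26 = 30 days in a 29-day window.
2. Give zero only when none of these supports is recorded.
3. Apply the death and ongoing-at-completion rules to the union, so that a subject who dies while on any of these supports is carried to Day 29 whether or not an oxygen stop date exists.
4. Use Ordinal categories 2-4 only as an in-hospital cross-check. Oxygen used after discharge falls in category 6 or 7 and would be missed.

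The cost is SAP wording and programming. Oxygen and ventilation dates (SAP 6.2), extracorporeal-support dates (SAP 7.5) and the in-hospital daily Ordinal scale are already collected. If sites already enter ventilation as oxygen, the union leaves those days unchanged. The downside is some added overlap with ventilation duration, which is still reported separately.
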